12.3. Expectedness

An expected adverse reaction is an adverse reaction, the nature or severity of which is consistent with the applicable product information (Investigator's Brochure [8]), otherwise it is considered unexpected.

Based on non-clinical safety data in experimental animals as well as on Phase 1 data in healthy male volunteers and in patients with advanced PD (Phase 2a), AEs are likely to predominantly be CNS related. Adverse reactions in patients with advanced PD are listed below:

Table 4: Potential AEs associated with mesdopetam treatment	

Nervous system	Cardiac	General disorders and administration site condition	Musculoskeletal and connective tissue disorders
Parkinsonism	Postural dizziness	Lethargy	Muscular weakness
Tremor	Dyspnoea	Fatigue	
Muscular rigidity		Oedema	
Insomnia			
Somnolence			
Headache			
Slurred thinking			
Dissociation			
Balance disorder			
Dizziness			
			I
Confidential		Version: 5.0	

Confidential	Version: 5.0	Page 56 of 74
Protocol: IRL790C005	Date: 5 Mar 2021	6

Nervous system	Cardiac	General disorders and administration site condition	Musculoskeletal and connective tissue disorders
Concentration difficulties			
Gait freezing			
Fall			

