12.2. Definitions

Adverse Event (AE)

Untoward medical occurrence in a patient administered a pharmaceutical product and that does not necessarily have a causal relationship with this treatment.

An AE can therefore be any unfavourable and unintended sign (including laboratory abnormal finding), system or disease temporally associated with the use of the medicinal product, whether or not considered as related to the IMP.

Adverse Drug Reaction (ADR)

Untoward and unintended responses to an IMP related to any dose administered.

All AEs judged by either the reporting Investigator or the Sponsor as having a reasonable causal relationship to a medicinal product qualify as adverse reactions. The expression "reasonable causal relationship" means to convey in general that there are facts or evidence meant to suggest a causal relationship.

Serious Adverse Event (SAE)

Untoward medical occurrence or effect that at any dose falls in one or more of the following categories:

- Results in death
- Is life-threatening
- Requires hospitalisation or prolongation of existing inpatients' hospitalisation. Hospitalisation refers to a situation whereby an AE is associated with unplanned overnight admission into hospital.
- Results in persistent or significant disability or incapacity
- Is a congenital anomaly or birth defect

Confidential	Version: 5.0	Page 55 of 74
Protocol: IRL790C005	Date: 5 Mar 2021	5

Other important medical events that may not be immediately life-threatening or result in death or hospitalization but, when based on appropriate medical judgment, may jeopardize the subject or may require intervention to prevent one of the outcomes in the definition of SAE listed above. Medical and scientific judgment should be exercised in deciding whether expedited reporting is appropriate in such situations.

Planned hospitalisations or surgical interventions for a condition that existed before the patient signed the ICF and that did not change in intensity are not SAEs.

Unexpected Adverse Event (UAE)

When the nature or severity of an AE or SAE is not expected based on the information provided in the IB, it is an unexpected AE or SAE. The Sponsor or designee is responsible for determining the expectedness of an AE.

Suspected Unexpected Serious Adverse Reactions (SUSARs)

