SUSARs are AEs that are suspected to be related to the IMP (i.e. AEs assessed as possibly, probably or definitely related according to Section 12.5) and are both unexpected and serious. The Sponsor or designee is responsible for determining whether a reported SAE meets the definition of a SUSAR.

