12.5. Causality assessment

The Investigator must assess the causal relationship between an AE and the IMP using the definitions below and record it on the AE Form in the CRF as well as on the SAE Report Form, if applicable:

- *Probable* the AE has a strong temporal relationship to the IMP or recurs on rechallenge, and another aetiology is unlikely or significantly less likely
- *Possible* the AE has a suggestive temporal relationship to the IMP, and an alternative aetiology is equally or less likely
- *Not related* the AE has no temporal relationship to the IMP or is due to underlying/concurrent illness or effect of another drug (that is, there is no causal relationship between the IMP and the AE)

Confidential	Version: 5.0	Page 57 of 74
Protocol: IRL790C005	Date: 5 Mar 2021	5

An AE is considered causally related to the use of the IMP when the causality assessment is probable or possible.

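### Protocol 12.2 and 12.3 give conflicting expectedness rules, so whether a listed reaction at a severity the Investigator's Brochure does not describe is a SUSAR depends on which section is applied

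*Protocol*

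**What the plan says.** Two places in the protocol define expectedness, both by reference to the IB.

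- Section 12.2, under Unexpected Adverse Event: "When the nature or severity of an AE or SAE is not expected based on the information provided in the IB", the event is unexpected.
- Section 12.3, Expectedness: "An expected adverse reaction is an adverse reaction, the nature or severity of which is consistent with the applicable product information"; "otherwise it is considered unexpected".

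The last definition in 12.2 is that of a SUSAR: an event suspected to be related to the IMP, where such events "are both unexpected and serious". The seriousness criteria in 12.2 include "Results in death" and "Is life-threatening". The sponsor or its designee decides both expectedness and SUSAR status.

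The SUSAR definition describes the qualifying causality grades as "AEs assessed as possibly, probably or definitely related according to Section 12.5". Section 12.5 has three grades: probable, possible and not related. It states: "An AE is considered causally related to the use of the IMP when the causality assessment is probable or possible".

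Table 4, in section 12.3, lists adverse reactions in patients with advanced PD as terms only, with no grade or severity.

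**The concern.** Section 12.3 turns the 12.2 sentence from unexpected to expected but keeps the word *or*. Negating an *or* condition gives an *and* condition, so the two sections are not complements. Both are operative text in Version 5.0, and neither is said to take precedence.

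The classification has consequences. Under section 12.10 the CRO reports SUSARs to the competent authority and the ethics committees. Under section 12.9 investigators are kept informed of SUSARs, and suspension of the trial because of a SUSAR is foreseen. An assessor looking up expectedness could reasonably go to the section with that title, which holds the looser rule. A related serious event could then be left out of these reports and notifications although 12.2 would include it, or two assessors could classify the same event differently.

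**Working it through.** There is no sample size, power or rate to recompute. The check is a truth table.

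**Inputs.** Let N mean that the nature of the event matches the IB, and S that its severity matches the IB.

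- Section 12.2: unexpected = (not N) or (not S). Hence expected = N and S.
- Section 12.3: expected = N or S. Hence unexpected = (not N) and (not S).

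Section 12.2 speaks of AEs and SAEs, and 12.3 of adverse reactions. For the SUSAR decision this difference does not matter, because a SUSAR must already be suspected to be related.

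| Nature matches | Severity matches | Under 12.2 | Under 12.3 | Agree? |
|---|---|---|---|---|
| yes | yes | expected | expected | yes |
| yes | no | unexpected | expected | **no** |
| no | yes | unexpected | expected | **no** |
| no | no | unexpected | unexpected | yes |

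**Result.** The sections agree in 2 of 4 combinations and disagree in 2 of 4. Section 12.2 leaves three combinations unexpected and 12.3 leaves one. These are counts of logical cases and say nothing about how often each would occur.

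**Which disagreement matters in practice.** In the third row the nature of the event is not in the IB. A brochure ordinarily gives severity for the reactions it describes, so there would usually be no listed severity for such an event to match. The second row is the practical one: the reaction is listed, but it occurs at a severity the IB does not describe.

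**Worked case.** Take a related, life-threatening fall, and assume the IB lists falls but describes no life-threatening ones.

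1. Serious: yes, since life-threatening events meet the 12.2 criteria.
2. Related: yes, by assumption.
3. Unexpected under 12.2: yes, because severity does not match. The event is a SUSAR.
4. Unexpected under 12.3: no, because nature matches. The event is not a SUSAR.

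**How many terms could be involved.** Table 4 has 13 nervous system, 2 cardiac, 3 general and 1 musculoskeletal term: 13 + 2 + 3 + 1 = 19. This counts the terms in the table. The number affected depends on the severities the IB describes for each, which cannot be seen here.

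**Causality cross-reference.** The SUSAR definition names possible, probable and definite. Section 12.5 counts possible and probable as related and has no definite grade. The extra word matches nothing, and both related grades are covered, so no event is lost.

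**The case against.** The strongest reply is that the SUSAR definition sits in 12.2, directly after the definition of an unexpected event. Read in place, its use of unexpected is the 12.2 meaning, under which a severe form not described in the IB is a SUSAR. Expectedness is decided by the sponsor or its designee rather than by sites, and section 12.10 ties SUSAR reporting to the applicable regulatory requirements. Nothing in the documents shows that 12.3 alone would be used. This stands as far as it goes: it makes 12.2 a natural reading, but it does not remove the conflicting rule in 12.3.

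Other safeguards do not depend on expectedness. Section 12.9 sends every SAE to the CRO and sponsor within 24 hours, whatever the causality. It also requires new safety information that would adversely affect patients to be reported to authorities, ethics committees and investigators, with no condition on SUSAR status. The annual safety report (25.2) summarises all SAEs. This stands too, and it limits what is at stake.

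A reader might infer more than the documents support:

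- *That severe forms of listed reactions will drop out of SUSAR reporting.* This follows only if 12.3 is applied in preference to 12.2.
- *That 12.3 is the reverse of 12.2.* The truth table shows agreement when both attributes match and when neither does.
- *That any grade 4 or 5 case of a Table 4 term is affected.* This would need the IB. The one grade distribution in section 4.6 (74% grade 1, 26% grade 2) is for treatment-emergent events in healthy male volunteers, whereas Table 4 concerns patients with advanced PD. For the phase 1b and 2a studies the protocol says only that events were generally mild.
- *That SUSAR reporting is a main way a severe signal reaches anyone able to act, because SAP section 8 plans no DSMB analyses.* The sponsor receives every SAE and, under section 23, can stop the study.
- *That Table 4 is itself the standard for expectedness.* Section 12.3 names the IB as the reference.

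**Conclusion.** The inconsistency is real and follows from the text alone. Sections 12.2 and 12.3 disagree when exactly one of nature and severity matches the IB, in practice when a listed reaction occurs at an undescribed severity. If such an event is serious and related, it is a SUSAR under 12.2 and is not one if 12.3 is applied. What is exposed is SUSAR reporting to authorities and ethics committees and SUSAR notification to investigators; the sponsor and CRO learn of the event in either case.

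The frequency cannot be estimated. It depends on the severities described in the IB, and on which section the assessor applies, which the protocol does not settle. The point touches no endpoint, analysis, sample size or dosing rule. It still merits correction, because it concerns a rule that feeds regulatory reporting and the remedy is a few words. The unmatched causality grade is a tidying matter only.

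**What to change.** 1. In section 12.3, reword the first sentence so that a reaction is expected only when its nature **and** its severity are both consistent with the Investigator's Brochure, and is otherwise unexpected. This makes 12.3 the exact complement of 12.2.
2. As a minor clean-up, have the SUSAR definition in 12.2 refer only to the two related grades in 12.5, possible and probable.
3. Check that the safety management plan, if it restates the rule, uses the corrected form.

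The cost is two sentences in a protocol amendment and one document check. There is no effect on design or analysis. The only operational consequence is possibly a few more expedited reports, and only if 12.3 as it stands was being applied.

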12.4. Intensity of adverse event

The grading of the severity of AEs will follow the Common Terminology Criteria for Adverse Events (CTCAE) v5.0 [13]. Grade refers to the severity of the AE. The CTCAE displays Grades 1 through 5 with unique clinical descriptions of severity for each AE based on this general guideline.

The Investigator must assess the severity of an AE using the following definitions, and record it on the AE Form in the CRF:

Grade 1	Mild; asymptomatic or mild symptoms; clinical or diagnostic observations only; intervention not indicated.
Grade 2	Moderate; minimal, local or non-invasive intervention indicated; limiting age-appropriate instrumental Activities of Daily Living (ADL)*.
Grade 3	Severe or medically significant but not immediately life-threatening; hospitalisation or prolongation of hospitalisation indicated; disabling; limiting self-care ADL**.
Grade 4	Life-threatening consequences; urgent intervention indicated.
Grade 5	Death related to AE.

* Instrumental ADL refer to preparing meals, shopping for groceries or clothes, using the telephone, managing money, etc.

**Self-care ADL refer to bathing, dressing and undressing, feeding self, using the toilet taking medications, and not bedridden.

12.5. Causality assessment

The Investigator must assess the causal relationship between an AE and the IMP using the definitions below and record it on the AE Form in the CRF as well as on the SAE Report Form, if applicable:

- *Probable* the AE has a strong temporal relationship to the IMP or recurs on rechallenge, and another aetiology is unlikely or significantly less likely
- *Possible* the AE has a suggestive temporal relationship to the IMP, and an alternative aetiology is equally or less likely
- *Not related* the AE has no temporal relationship to the IMP or is due to underlying/concurrent illness or effect of another drug (that is, there is no causal relationship between the IMP and the AE)

Confidential	Version: 5.0	Page 57 of 74
Protocol: IRL790C005	Date: 5 Mar 2021	5

An AE is considered causally related to the use of the IMP when the causality assessment is probable or possible.

12.6. Action taken regarding the IMP

The action taken regarding IMP must be described by selecting one of the following:

- Permanently discontinued
- Stopped temporarily
- Dose reduced
- No action taken
- Unknown/not applicable

12.7. Outcome

The Investigator must assess the outcome of an AE using the definitions below and record it on the AE Form in the CRF:

- *Recovered* the patient has recovered completely, and no symptoms remain
- *Recovering* the patient's condition is improving, but symptoms still remain
- *Recovered with sequelae* the patient has recovered, but some symptoms remain (for example, the patient had a stroke and is functioning normally, but has some motor impairment)
- *Not recovered* the patient's condition has not improved, and the symptoms are unchanged (for example, an atrial fibrillation has become chronic)
- Death

12.8. Recording adverse events

AEs identified using any of the following methods will be recorded:

AEs spontaneously reported by the patient

AEs observed by the Investigator or medical personnel

AEs elicited based on non-leading questions from the Investigator or medical personnel

Collection of AEs starts after the patient signs the ICF and continues until the last follow-up assessment. Any AE with start date on the day of first IMP administration must be recorded with start time.

At the follow-up visit, information on new AEs or SAEs, if any, and stop dates for AEs recorded and on-going during the dosing period must be recorded. AEs must be followed up until resolution or the follow-up assessment, whichever comes first.

AEs must be recorded on an AE Form in the CRF. The Investigator must provide information on the AE, preferably with a diagnosis or at least with signs and symptoms; start and stop

Confidential	Version: 5.0	Page 58 of 74
Protocol: IRL790C005	Date: 5 Mar 2021	5

dates, start and stop times (only applicable for AEs with start date on the day of first IMP administration); intensity; causal relationship to IMP; action taken, and outcome.

If the AE is serious, this must be indicated on the AE Form in the CRF. Furthermore, the Investigator must fill out the SAE Report Form and report the SAE to Worldwide Clinical Trials as described in Section 12.9.

AEs, including out-of-range clinically significant safety laboratory values, must be recorded individually, except when considered manifestations of the same medical condition or disease state; in such cases, they must be recorded under a single diagnosis.

If the severity/intensity of an AE increases a new AE Form must be completed in the CRF.

Patients with AEs occurring during the study must be treated according to clinical practice at the discretion of the Investigator.

It is the responsibility of the Investigator to follow up on all SAEs until the patient has recovered, stabilized, or recovered with sequelae and to report to the Sponsor all relevant new information using the same procedures and timelines as those for the initial report. Relevant information includes discharge summaries, autopsy reports, and medical consultation.

The SAE reporting period starts at the time of the signature of the ICF until 30 days after the last follow-up visit. SAEs spontaneously reported by a patient to the Investigator within 30 days after the last follow-up assessment must be handled in the same manner as SAEs occurring during the study. These SAEs will be reported to the Sponsor.

12.9. Serious adverse Events

All SAEs must be reported to the Clinical Research Organisation (CRO) and Sponsor immediately and within 24 hours of awareness, regardless of causal relationship. An SAE form must be filled in by a member of the research team and kept in the Trial Master File (TMF).

All SAEs occurring until the end of the trial must be reported by fax and/or email immediately by the Investigator or designated assistant is made aware of the event and by full report as soon as possible thereafter.

All SAEs must be emailed or faxed to Worldwide Clinical Trials: **Email:** [contact]

Fax number: Fax US: [name], Fax ROW: [contact]

Pregnancies occurring during the study must be reported immediately by email or fax using the Pregnancy Form.

The Sponsor and Worldwide Clinical Trials will keep the Investigator informed of all SUSARs reported to them for the product under investigation, from anywhere in the world, for the duration of the trial at a frequency appropriate to the trial.

In addition, any new safety information that would adversely affect the safety of patients or the conduct of the trial will be reported by IRL to the CAs, IECs/IRBs and Investigators. If the trial is to be suspended as a result of a SUSAR, or due to any urgent safety measure taken, the CA and IECs/IRBs will be notified as soon as possible and within three days of the decision.

Confidential	Version: 5.0	Page 59 of 74
Protocol: IRL790C005	Date: 5 Mar 2021	č

The Sponsor will submit Safety Reports to the CAs and IEC/IRBs annually or more frequently if so requested.

12.10. Reporting of SUSARs

Worldwide Clinical Trials will report SUSARs occurring in the trial to the CA and to the relevant Independent Ethics Committees (IEC(s))/Institutional Review Boards (IRB(s)) in line with the applicable regulatory requirements.

13.DATA MANAGEMENT

Data will be recorded on a CRF by the Investigator (or designee). The database, data entry and electronic checks will be developed using a Clinical Database Management System. Computerized data cleaning checks will be used in addition to manual review to check for discrepancies and to ensure consistency and completeness of the data. An electronic audit trail system will be used to track all data changes in the database.

Data clarification queries will be generated electronically in order to clarify any issues which arise regarding the data entered into the CRF and database.

Quality control check of the data entry will be performed on the CRFs.

Medical history findings and AEs will be coded using the MedDRA dictionary; medications will be coded using the World Health Organisation Drug dictionary.

13.1. Trial documentation and trial confidentiality

13.1.1. Trial documentation, CRFs and document keeping

The Investigator must generate and maintain adequate records (patient medical records, CRFs, source documents) to enable the conduct of this trial to be fully documented. Each patient enrolled into the trial must have a CRF completed and the CRF must be reviewed and signed off by the Investigator. This applies to those patients who failed to complete the trial (even during the pre-randomization period). CRFs are to be completed either at the time of the patient's visit or as soon as possible after the visit (no later than 72 hours) so that they always reflect the latest observations on the patients participating in the study. The Investigator must verify that all data entries in the CRFs are accurate and correct. The nature and location of all source documents will be identified to ensure that all sources of original data required to complete the CRF are known to the investigational staff and are accessible for verification by the clinical monitor. If electronic records are maintained, the method of verification must be discussed with the investigational staff. A source data verification (SDV) log will be prepared by the CRO. This will describe the proportion of CRF data that will be verified by the monitor against the patients' medical records and source data.

The author of an entry in the source documents must be identifiable. Direct access to source documentation (medical records) must be allowed for the purpose of verifying that the data recorded on the CRF are consistent with the original source data. The possibility to access source documents during remote monitoring, is regulated as per local requirements.

Confidential	Version: 5.0	Page 60 of 74
Protocol: IRL790C005	Date: 5 Mar 2021	

If data are recorded directly into the CRF, there should be, at a minimum, an entry in the medical record that each of the assessments was performed, who performed it and the date it was done. Source documents will be created and maintained in accordance with ALCOA-C (Attributable, Legible, Contemporaneous, Original, Accurate, Complete) criteria that is the standard for data integrity.

The CRF will be compared with the source documents to ensure that there are no discrepancies between critical data. All entries, corrections, and alterations are to be made by the responsible Investigator or an authorized member of the investigational staff.

Data clarification and query resolution will be conducted on an ongoing basis by the monitor and the contract data management company. The Sponsor will have overall responsibility for the data.

The Principal Investigator must be aware of their responsibility to retain patient identification codes in line with regulatory requirements after completion or discontinuation of the trial. If a patient ceases treatment prematurely, then the reason must be noted in the CRF. If a patient ceases treatment because of an AE, reasonable efforts must be made to clearly document the outcome.

The Principal Investigator will allow authorized Sponsor personnel, auditors and regulatory authorities direct access to the patients' medical records.

Copies of protocols, CRF page/printouts, originals of test results, reports, drug dispensing logs, correspondence, records of informed consent or other documents pertaining to the conduct of the trial must be kept on file by the Investigator in line with regulatory requirements or for the period of time specified by local law for the preservation of hospital patient documents, whichever is the longer. No trial documents should be destroyed without prior written agreement between Sponsor and the Investigator. Where storage at the centre is limited, the Sponsor may make arrangement for documents to be stored at an independent data archiving facility on behalf of the Principal Investigator. Should the Investigator wish to assign the trial records to another party, or move them to another location, the clinical trial monitor must be consulted.

